## 6. Reporting of Adverse Events or Unanticipated Problems

### PROTECTION OF HUMAN SUBJECTS

### **Risks to Human Subjects:**

Human Subjects Involvement, Characteristics, and Design: As many as 50% of ICU survivors aged 65 and older who had an episode of delirium are left with newly acquired “Post-Intensive care Syndrome” (PICS) characterized by cognitive, physical, or psychological symptoms that have onset in the peri-ICU period and persist among ICU survivors for a long period of time with some patients never recovering from such devastating symptoms. We are proposing a behavioral intervention targeting ICU older survivors who have experienced delirium as a means of improving cognitive and functional outcomes. ICU survivors with delirium constitute a growing segment of older American who are vulnerable to develop post ICU cognitive, physical, and psychological disability. The current system does not offer an effective recovery care for this population.

The target population is 344 English-speaking adults aged 50 and older who have been admitted to a critical care unit, have had at least one episode of delirium and are discharged home. This intervention targets cognitively impaired individuals suffering from delirium and will also include women and minorities who meet the inclusion criteria, as these vulnerable populations are at risk of Post-Intensive Care Syndrome.

Sources of Materials: During the hospital stay, research assistants will review the medical records and conduct delirium screening to assess the eligibility criteria for potential subjects. Furthermore, blinded assessors will complete the baseline assessment within the hospital or within the subject’s home as necessary. The data obtained from subjects will include self-report of demographics, health history, current medications, anxiety and mood symptoms, and quality of life questionnaire. The Assessors will also be collecting information on cognitive and physical performance via objective tests and physiologic status (blood pressure, height, weight, heart rate, oxygen saturation). Finally, the assessors will also conduct a medical record review to assess subject’s chronic conditions (Charlson index) and severity of medical illness (APACHE index). In addition to recording attendance, subject’s effort and use of modifications, the Trainers will be collecting information on RPE, heart rate and oxygen saturation, while Brain HQ will monitor cognitive performance, for each subject at each training session.

Data will be linked to participants through the use of a unique identifying number. Only persons on the research team will have access to the data. All data are collected for research purposes only. All data will be entered via a password-protected, study specific REDCap (Research Electronic Data Capture) database. Case Report Forms (CRFs) will be stored in locked filing cabinets at Regenstrief Institute. CRFs completed at non-affiliated institutions will be stored locally at their facility and, once the subjects are off-study, transferred to their long-term storage facility, per their local policy.

### **Potential Risks:**

(1) *Fatigue, anxiety, stress, or embarrassment from the training or testing sessions.* Emotional distress may result from answering health and behavior questions. Testing may also create anxiety, stress, or embarrassment at perceived performance. Participants may also become fatigued during the testing and/or training sessions.

(2) *Falls and/or muscle stiffness and soreness from exercise.* The exercise intervention components proposed in this study are consistent with standard recommendations for exercise among older adults. Based on piloting and published studies, the most common risk associated with increased exercise is mild muscle stiffness and soreness. Moderate-intensity physical activities are associated with a very low

risk of musculoskeletal complications. There is a low risk of fall given all exercises in the physical intervention are seated.

(3) *Cardiovascular complications from exercise.* The risks of cardiovascular complications do increase transiently during periods of strenuous physical activity.

(4) *Exposure of confidential information.* There is the potential for loss of privacy or confidentiality due to the data collection efforts of this study.

(5) *Discomfort with biological samples collection.* Two blood samples will be collected from each participant, one during their hospital stay and the other at 3-months follow-up. Drawing blood could be associated with pain, bruising, and anxiety.

**Adequacy of Protection Against Risks:**

Recruitment and Informed Consent: Eligible subjects will be identified through the intensive care units census to which they are admitted. Study personnel will consent the patient or their legally authorized representative (if the patient is unable to consent for themselves) during their ICU hospitalization. If LAR provides consent, study personnel will seek consent from subject when capacity is regained, either at hospital or home.

**Protections Against Risk:**

(1) *Fatigue, anxiety, stress, or embarrassment from the training or testing sessions.* All questions planned for this study are part of validated standardized instruments, and we are not asking any questions that do not directly relate to the study purpose. Both Interventionists and Assessors will be trained in their proper use and in the importance of privacy and sensitivity to the participant's time. They will be trained to be alert and sensitive to signs of fatigue and other symptoms and to take appropriate actions when they are present. Breaks from testing will be offered as needed; assessment sessions can also be split into two sessions if a participant is tired or physically uncomfortable.

(2) *Falls and/or muscle stiffness and soreness from exercise.* We have minimized the risk of a fall through the use of seated endurance exercise training; the stiffness and soreness from adoption of exercise training are minimized by the moderate nature of the exercise program; any soreness that may occur early in the training will subside within a few days and be unlikely to occur again with adherence. Participants with persistent or very severe soreness will be encouraged to contact their primary care provider. In the ~2,000 in-home assessments that we have done in the African-American Health study which has an extensive physical exam protocol, we have not had a single fall or other adverse event. We attribute this to our very careful training and supervision procedures, which we will also be using in the proposed trial. We will have an emergency plan in place to handle any emergencies that might occur.

(3) *Cardiovascular complications from exercise.* We have incorporated exercise program elements that are associated with lower risks of cardiovascular complications, such as employing a warm up, flexibility exercise, using moderate intensity exercise, and a gradual progression of exercise intensity and duration. Supervised exercise programs also have a low rate of complications suggesting that the use of well-trained exercise instructors will also provide a margin of safety to the participants. Participants and interventionists will be instructed in the signs and symptoms of cardiovascular complications and how to respond to them both during the exercise sessions and at other times.

(4) *Exposure of confidential information.* Indiana University requires certification of training in protection of human subjects in research. The investigators, interventionists, assessors, and all key personnel have or will have successfully completed training and certification in these courses. All research involving the use of these data must be reviewed and approved by the IRB. We will assure the privacy of subjects and confidentiality of study data by assigning unique identifiers to track participants' data (rather than using names or hospital or social security numbers) and keep all records under lock with access only by study personnel. These procedures have been dutifully adhered to in prior studies. The final data files for this study will be merged, maintained, and analyzed on servers managed by the Division of Biostatistics, Department of Medicine, Indiana University School of Medicine. This group has extensive experience in the handling and security of PHI. None of the individual participant data will be identifiable in published reports or manuscripts and the analyzable datasets will not contain the participant's unique identifier.

(5) *Discomfort with biological samples collection.* A small amount of blood will be required (maximum 44 ml over the entire study course) for the specified laboratory analyses. We will attempt to coordinate all blood sampling with that done for clinical purposes or from indwelling catheters to avoid added venipuncture. Sample collection at 3-month's follow-up will be performed by an experienced phlebotomist. We have collected blood samples at homes of our participants in our other projects and have not encountered any serious adverse events. Blood will be stored in de-identified tubes and will be transported by personnel who have obtained certification in specimen handling and transfer. In addition we are planning to have continuous feedback from the patient, the caregiver, the physician, and the nursing staff to discuss any problems encountered during the data collection.

#### **Potential Benefits of Proposed Research to Human Subjects and Others.**

The study participants will be engaged in national health guideline-level physical activity with all its attendant positive results (e.g., decreased fall risk, improved cardiovascular function, improved strength, improved pulmonary capacity, potentially reduced insulin resistance). Participants will also receive small payments for participation. This research could also provide a non-pharmacological treatment for cognitive impairment in patients suffering from ICU acquired cognitive impairment. Despite the high prevalence rates of cognitive and physical disability among ICU survivors, only ICU patients who survived major stroke, traumatic brain injury, or cardiac surgery receive formal cognitive or physical rehabilitation leaving a large percentage of ICU survivors with no such rehabilitation and higher risk for hospital readmission or death.

The intervention proposed in this study builds on prior research and may hold promise for an effective and scalable recovery model for this population. This intervention does require additional resources that will cost additional money; however, it is possible that these short-term costs will be offset by reductions in overall costs to patients and the healthcare system. Patients enrolled in our study and randomized to receive our proposed intervention might have a reduction in post-ICU symptoms and, subsequently, may experience improved cognitive and physical function, improved mood, and quality of life. Our intervention might also improve other health outcomes such as a lower rate of hospital acquired complications, a higher probability of survival, lower institutionalization rates, and decreased length of hospital stay, thereby decreasing health care utilization and cost. The intervention may delay onset of Alzheimer's disease and related dementias among ICU survivors.

#### **Importance of Knowledge Gained.**

Up to 70% of ICU survivors aged 65 and older develop long-term cognitive impairment and other functional and psychological sequelae of critical illness. Currently there are no effective and scalable recovery models to remediate or treat ICU acquired cognitive impairment and its deleterious effects on

quality of life and independence of the growing segment of ICU survivors. Our proposed intervention may provide a conceptual and scalable recovery model to remediate or treat post-delirium cognitive impairment and its deleterious effects on quality of life and independence of the growing segment of ICU survivors.

## 7. Study Withdrawal/Discontinuation

Participants who wish to withdraw from the study will notify the study team verbally or via letter as outlined in the HIPAA authorization document.

## 8. Statistical Considerations

To verify the comparability of the randomized groups, patients' baseline characteristics among the four groups will be compared using analysis of covariance (ANCOVA) for continuous variables and the Cochran-Mantel-Hansel statistic for categorical variables while adjusting for age group. We will examine the distributions of continuous variables and use alternative approaches such as transformation or nonparametric methods in cases of violation to the normal distribution assumption. We will also examine the frequency distribution of all categorical variables and adopt exact inference procedures in cases of zero or small cell size. All analyses will be conducted using the SAS 9.4 (SAS Institute, Carey, North Carolina).

**Primary Specific Aim:** Mixed effects models will be used with repeated RBANS scores collected at baseline, 3 months and 6 months as the outcome measures, group, time and a group by time interaction as independent variables while adjusting for stratification variables and other potential baseline covariates found to be significantly different in univariate comparisons. A significant interaction between group and time would indicate differences in changes of cognitive functions over time among the four groups. Post-hoc comparisons will be conducted following a significant interaction between group and time to compare the effect of the combined training group to the other three groups (attention control, cognitive training only, and exercise only groups) at 3 month for immediate training effect and at 6 month for sustained training effect. Separate mixed effect models will also be used for repeated, Trail Making A&B, and Stroop Color and Word Test scores.

**Secondary Specific Aim 1:** Separate mixed effects models will be used with repeated measures (SPPB, 2-minutes step, PHQ-9, GAD-7, SF-36 PCS and MCS) as the outcome variables, group, time and interactions between group and time as independent variables while adjusting for stratification variables and other baseline covariates that may be different among the four groups. Significant interactions between group and time in these models would indicate differences in changes of functional outcomes, depressive symptoms, and anxiety levels or quality of life over time among the four groups. Post-hoc analyses will also be conducted following significant interactions in the mixed effects models to compare the combined training group to the other three groups and to determine how early a group difference can be detected and whether the effect extends beyond the training period.

**Exploratory Aim 1:** Changes in the serum levels of CRP, IL-1, IL-6, IL-8, TNF-  $\alpha$ , S-100 $\beta$ , GFAP, BDNF, VEGF, and IGF-1 will be calculated and used as the dependent variables in ANCOVA models with group as the independent variable and adjusting for stratification variables and baseline covariates that are

found to be different among the groups in univariate comparisons. Post-hoc comparisons will be used following a significant group effect to compare biomarker levels in the combined training group to the other three groups.

Missing Data: Two types of missing data are anticipated in this trial. The first is due to death during follow-up. Our previous studies on ICU survivors have shown that most post-ICU deaths happen within the first 30 days of discharge. We do not expect rates of death to differ among the four randomized groups. The second type of missing data comes from participant withdrawal during follow-up. There may be a potential for higher rate of withdrawal in those enrolled in the intervention groups than in the control group. The mixed effects model approach we propose to use is robust under the missing at random assumption, i.e. the probability of missing is unrelated to the missing observations. We will compare baseline characteristics of subjects with missing outcomes due to death or dropout during follow-up to detect potential violation to the missing at random assumption. Intention to treat analysis will be used in all models. Further sensitivity analyses will be performed using various methods of imputation or a full parametric likelihood approach assuming various patterns of missing data.

Sample Size and Power: Cognitive training had been found to have a moderate effect size of approximately 0.5 SD and the combined training was found to have a larger effect size of 0.9 SD when comparing to the control group in healthy elderly subjects. Assuming effect sizes of 0.4 SD in the cognitive training only group and the exercise only groups at 3 and 6 month post baseline compared to the attention control group and effect size of 0.8 SD in the combined training group at 3 and 6 month post baseline compared to the attention group, a sample size of 60 patients in each group will yield 83% power at detecting a significant group by time interaction in a mixed effect model adjusting for correlations of 0.2 for outcomes measured 3 month apart and correlations of 0.1 for outcomes measured 6 month apart at  $\alpha=0.05$ . The power estimation was conducted using the GLMPower procedure in SAS. To further assume that 30% patients may miss some post-baseline assessments, we will need to enroll a total of 344 patients into the study (86 patients per group). Outcomes in Secondary Aim 1 will also have 83% power to detect effect sizes similar to those described for the Primary Aim. For Secondary Aim 2, we will have 81.7% power to detect an overall treatment effect in changes in biomarkers with effect sizes of 0.31 SD in the cognitive training only and the exercise only groups and 0.62 SD in the combined training groups at  $\alpha=0.05$  using one-way ANOVA and the Power procedure in SAS.

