Our team is proposing a 2x2 factorial design randomized controlled trial (RCT) called "Decreasing Alzheimer's Disease and Related Dementias after Delirium-Exercise and Cognitive Training (DDD-ECT)" to evaluate the efficacy of 12 weeks of combined physical exercise and cognitive training on the primary outcome of cognitive function among older ICU survivors who experienced delirium or subsyndromal delirium during their ICU stay. We propose to deliver these interventions via a facilitator-led, small group format using internet-enabled, multiparty-videoconference delivered directly into the participants' homes to achieve the following aims:

**Primary Specific Aim: Determine the effect of the combined physical exercise and cognitive training on the cognitive function of ICU survivors aged 50 and older.** Hypothesis: In comparison to older ICU survivors randomized to attention control or either intervention alone, those randomized to 12 weeks of combined physical exercise and cognitive training will have higher total index cognitive scores as assessed by the Repeatable Battery for the Assessment of Neuropsychological Status (RBANS) at 3 and 6 months post randomization.

**Secondary Specific Aim 1: Determine the effect of the combined physical exercise and cognitive training on physical performance, anxiety and depressive symptoms, and quality of life of ICU survivors aged 65 and older.** Hypotheses: In comparison to older ICU survivors randomized to attention control or either intervention alone, those randomized to 12 weeks of combined physical exercise and cognitive training will have higher physical performance as measured by short physical performance battery (SPPB) and two-minute step test, lower mood and anxiety symptoms as measured by Patient Health Questionnaire (PHQ-9) and Generalized Anxiety Disorder (GAD-7) scale, and higher quality of life as measured by the Medical Outcomes Study 36-item short form (SF-36) at 3 and 6-months post randomization.

**Exploratory Aim 1: To examine the mechanisms of action of combined training.** Hypothesis: At the completion of treatment, the combined intervention group will show reduced serum levels of CRP, IL-1, IL-6, IL-8, TNF- $\alpha$ , S-100 $\beta$ , and GFAP and increased levels of BDNF, VEGF, and IGF-1 compared to the attention control, or either intervention alone groups.

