### **Randomization:**

[figure not shown]
After obtaining an informed consent, study staff will complete a baseline assessment consisting of measures of cognition, physical function, depression and anxiety, and quality of life (see measures section 4.3.l. below). Blood samples will also be collected from the participants at the time of baseline assessment. Baseline may be completed at subject's home after hospital discharge if unable to complete full assessment in the hospital. After initial assessment, study subjects will be randomized to study groups. Randomization will be stratified by discharge location (home, other facility) and managed by the IU site

[During COVID-19 health crisis, baseline assessments will be completed via phone; abbreviated measures of cognition, and no measures of physical function will be obtained due to the limitations of phone administration. Blood samples will not be collected.]

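### The primary group-by-time test gives each arm its own baseline RBANS mean although baseline precedes randomization; at the plan's assumed correlations it keeps about 45% of the information of a baseline-constrained test

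*Combined protocol and SAP*

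**What the plan says.** Section 8, Primary Specific Aim, fits a mixed effects model to "repeated RBANS scores collected at baseline, 3 months and 6 months as the outcome measures, group, time and a group by time interaction". Its test is the interaction: "A significant interaction between group and time would indicate differences in changes of cognitive functions over time among the four groups". Comparisons of the combined arm with the other three, at 3 and at 6 months, follow only if that interaction is significant. The secondary outcomes use models of the same form.

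Section 4 fixes the order of events: "After initial assessment, study subjects will be randomized to study groups". Under its COVID-19 provision, "baseline assessments will be completed via phone; abbreviated measures of cognition" replace the full battery.

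The sample size paragraph of Section 8 gives 83% power for the interaction with 60 per group, "adjusting for correlations of 0.2 for outcomes measured 3 month apart and correlations of 0.1 for outcomes measured 6 month apart". The hypothesis in Section 2 is that the combined arm "will have higher total index cognitive scores" at 3 and 6 months.

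For Exploratory Aim 1, changes in serum markers "will be calculated and used as the dependent variables in ANCOVA models with group as the independent variable". Covariates are added only where the arms are found to differ at baseline.

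**The concern.** Group plus group-by-time, with baseline among the responses, gives every arm its own baseline mean. Because baseline is measured before randomization, those four true means are identical. Estimating them separately makes the interaction a test on changes from baseline, and at low correlations a change score carries much of the baseline measurement as noise. The clause on adjusting for unbalanced covariates does not help, since baseline RBANS is already an outcome.

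The interaction is the gate to every comparison that answers the primary aim, so power lost there is lost for the whole aim. The plan also does not say what the comparisons at each visit are. Changes from baseline and differences in visit means are different estimators with different precision, and the wording in Section 2 fits either.

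**Working it through.** **Inputs (Section 8, sample size paragraph).** 60 per group, SD 1, two-sided 0.05. Effects against attention control are 0, 0.4, 0.4 and 0.8 SD at both visits. Correlations are 0.2 for baseline–3 months and 3–6 months, and 0.1 for baseline–6 months.

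**Between-arm sum of squares.** The mean effect is 0.4, so 60 × (0.4² + 0 + 0 + 0.4²) = 60 × 0.32 = 19.2. The noncentrality is λ = 19.2 × 1'S⁻¹1, where S is the 2×2 covariance of the quantities tested. Both tests have 6 df.

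**Planned test (changes from baseline).** Variances are 2(1 − 0.2) = 1.6 and 2(1 − 0.1) = 1.8; the covariance is 1 + 0.2 − 0.2 − 0.1 = 0.9.
- 1'S⁻¹1 = (1.6 + 1.8 − 2 × 0.9)/(1.6 × 1.8 − 0.9²) = 1.6/2.07 = 0.773
- λ = 14.84; F(6, 468) power = 83.3%

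This reproduces the stated 83%. Other common versions of the interaction test give 82.4% to 84.7%, so the plan powers exactly the unconstrained test it describes.

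**Common baseline mean.** With complete data this equals conditioning on baseline. Variances are 1 − 0.2² = 0.96 and 1 − 0.1² = 0.99; the covariance is 0.2 − 0.2 × 0.1 = 0.18.
- 1'S⁻¹1 = (0.96 + 0.99 − 0.36)/(0.96 × 0.99 − 0.18²) = 1.59/0.918 = 1.732
- λ = 33.25; power = 99.7%

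Information kept by the planned test: 0.773/1.732 = 0.446. About 28 evaluable per group would give the constrained test the power that the plan obtains with 60. A joint test ignoring baseline altogether has λ = 19.2 × 2/1.2 = 32.0, so at these correlations the planned use of baseline does worse than discarding it.

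**Simulation.** Two runs of 4,000 trials gave power of 82.8% and 81.7% as planned, against 99.6% and 99.8% baseline-adjusted. Type I error was 5.1% and 4.9%, against 5.4% and 5.1%.

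**Other correlations (illustrative, not in the documents).**

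| Correlations 3/6 months apart | λ planned | λ constrained | Loss | Power planned | Power constrained |
|---|---|---|---|---|---|
| 0.2/0.1 (plan) | 14.8 | 33.3 | 55% | 83% | 99.7% |
| 0.5/0.4 | 22.9 | 35.2 | 35% | 96.5% | 99.8% |
| 0.7/0.6 | 36.0 | 45.7 | 21% | 99.8% | 99.99% |
| 0.8/0.7 | 51.2 | 59.4 | 14% | >99.9% | >99.9% |

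**Comparisons at one visit.** With r the correlation of that visit with baseline, the relative variance is 2(1 − r) for change, 1 for the visit mean and 1 − r² for the constrained model. The last is never larger, because 2(1 − r) − (1 − r²) = (1 − r)² ≥ 0. For combined against a single intervention (0.4 SD, 60 per group) at the plan's correlations:
- Read as change: loss 40% at 3 months and 45% at 6 months; power 41% against 61%, and 37% against 59%.
- Read as visit means: loss 4% and 1%; power 59% against 61%, and 59% against 59%.

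At 0.5/0.4 the losses are 25% and 30% as change, and 25% and 16% as visit means. At 0.7/0.6 they are 15% and 20%, and 49% and 36%.

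**Missing baseline RBANS.** Shares of 10%, 20% and 30% are assumed; the documents give none. With both follow-ups present and data missing at random, at 0.2/0.1:
- Planned: λ = 13.71, 12.53, 11.27; power 80%, 75%, 70%
- Constrained: λ = 33.13, 33.00, 32.88; power 99.7% throughout
- Baseline as covariate, complete cases only: λ = 29.93, 26.60, 23.28

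**Biomarkers.** No correlation is given. If r is 0.2, 0.5 or 0.8, the variance of raw change against baseline-adjusted change is 1.6 v 0.96, 1.0 v 0.75 or 0.40 v 0.36.

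**The case against.** The strongest reply is that nothing here is in error. The test is valid, the power statement matches it, and a more efficient alternative is an improvement rather than a correction. That stands as a description of the fault.

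The omnibus harm also depends on the low assumed correlations. At 0.5/0.4 the chance of missing the assumed effects is about 3.5% against 0.2%, and above that the difference is negligible. Equal effects at both visits is, moreover, close to the least favourable pattern for the planned test: the kept fraction can range from 0.443 to 1. Both points are right. But 0.2/0.1 and equal effects are the plan's own inputs, so they are the fair basis for the headline.

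If the visit comparisons are differences in visit means, the loss at the plan's correlations is only 4% and 1%. That is so, but the plan does not say which they are, and at higher correlations the visit-mean reading loses most. The constrained model is at least as efficient on either reading.

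Finally, Sections 5 and 9 apply the phone provision to follow-up too, so some participants lacking a baseline RBANS may lack follow-up RBANS as well. If all of them did, constrained power at 10%, 20% and 30% would be 99.3%, 98.5% and 96.8% rather than 99.7%. The planned λ would fall as well, to 14.84 × 0.9, 0.8 and 0.7, or 13.36, 11.87 and 10.39. The gap remains. The biomarker point is exploratory and does not carry the grade.

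**Conclusion.** The concern holds. Under the plan's own assumptions, the test that gates all primary comparisons has a 17% chance of missing the assumed effects, against under 1% from the same data with a common baseline mean. This is inefficiency, not bias: a chance baseline imbalance is already reflected in the planned standard error, which it inflates.

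The 45% figure is for the joint test with complete data, equal effects at 3 and 6 months and correlations of 0.2/0.1. At higher correlations the omnibus test has ample power either way, and the gain lies mainly in the comparisons at each visit, whose definition the plan leaves open. Confidence in the algebra is high; the practical gain depends on the correlations actually observed. The change should be made.

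**What to change.** 1. For RBANS and the secondary repeated outcomes, specify a constrained longitudinal model: one baseline mean common to all arms, group effects only at 3 and 6 months, unstructured covariance.
2. Make the joint 6-df test of group differences at 3 and 6 months the primary test, and define the post-hoc contrasts as the adjusted group differences at each visit.
3. Restate power for that model.
4. State whether an abbreviated phone baseline counts as a missing RBANS total index.
5. Prefer this to a model with baseline as a covariate, which matches it only when every baseline is present and otherwise drops randomized participants.
6. In Exploratory Aim 1, include the marker's own baseline level as a fixed covariate in every ANCOVA of change.

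The cost is SAP wording, a new power calculation and a rule for phone baselines, with no new data. Because the primary test changes, the amendment should be final before any unblinded analysis. The only added assumption, equal baseline means, is guaranteed by randomization as long as baseline precedes it, as Section 4 states.
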